2.12. Protocol Section 9.3. Exposure and Compliance	
2.13. Protocol Section 9.6. Sample-Size Determination	11
2.14. Appendix 1. Schedule of Visits and Procedures for KGAA Addendum (11)	12
Acronyms	

1. Rationale for Addendum

The rationale for this addendum is to add the Q8W dosing regimen for lebrikizumab to Study J2T-DM-KGAA (KGAA) via extending the study treatment period by an additional 32 weeks beyond the main protocol.

This addendum will apply only to KGAA study participants who

- meet the addendum entry criteria, and
- are included in the study sites in the following countries:
 - o Australia
 - o Canada
 - o Korea
 - o Mexico
 - o Singapore
 - o Taiwan, and
 - o the United States.

See Section 2.1 of this addendum for rationale for including the Q8W dosing regimen for lebrikizumab.

2. Protocol Additions

The procedures described in this addendum are in addition to the requirements of the main KGAA protocol, unless otherwise specified. Some of the information is repeated from the main KGAA protocol for clarity. The original section numbers from the protocol are included in the addendum headings for ease of reference.

2.1. Protocol Section 1.4. Rationale for Dose and Treatment Regimen

To date, the Q8W dosing regimen of lebrikizumab has not been evaluated in clinical trials.

This proposed dosing regimen was selected for this addendum based on the AD Phase 3 data, including the PK-PD modeling for efficacy in AD.

Lebrikizumab demonstrated a durable treatment effect in the Phase 3 AD studies. In addition, the placebo (lebrikizumab withdrawal) arm in the maintenance period exhibited a durable and prolonged efficacy response after the last dose of lebrikizumab at Week 14, with a slow and gradual decline in response noted by Week 52.

These Phase 3 clinical data, together with the long half-life of lebrikizumab (mean = 24.5 days), prompted Lilly to evaluate a 250 mg Q8W dosing frequency CCI

2.2. Protocol Section 2. Study Objectives and Endpoints

The primary objective of this addendum is to assess efficacy of lebrikizumab 250 mg Q4W and Q8W during the additional 32 weeks of extension treatment. The endpoints for this addendum include

- proportion of patients who achieve IGA 0 or 1 at Week 32, and
- proportion of patients who achieve EASI-75 (≥75% reduction in EASI from baseline of parent study) at Week 32.

E. Handling of ICEs:

- a. Treatment discontinuation due to lack of efficacy: composite strategy. Patients who discontinue treatment due to lack of efficacy will be considered as treatment failures (non-responders).
- b. Treatment discontinuation due to any other reasons: a hypothetical strategy will be used to estimate what the response would have been if subjects continued with treatment.
- c. Dose modification to lebrikizumab 250 mg Q2W: composite strategy. Patients whose dose is modified to lebrikizumab 250 mg Q2W will be considered as treatment failures (non-responders).

2.3. Protocol Section 3. Study Design

Eligible patients will enter this 32-week open-label extension of the study and will be randomly assigned to the following lebrikizumab treatment groups, regardless of their previous treatment regimen (that is, Q2W or Q4W):

- lebrikizumab 250 mg Q4W, or
- lebrikizumab 250 mg Q8W

See Section 2.5 of this addendum for randomization ratio and stratification factors.

Patients who complete this study addendum or who terminate early will return to the clinic for a safety follow-up visit 12 weeks after the last study drug injection.

A patient is considered to have completed the study addendum if he/she has completed all required phases of the study, including the last visit as shown in the Schedule of Visits and Procedures of this addendum (Section 2.14).

[figure not shown]
The end of the study for participants in the KGAA addendum (11) is defined as the date of the last visit of the last patient in the study shown in the Schedule of Visits and Procedures for this addendum.

Dose modification

Starting from Visit 201, patients enrolled in this study addendum who do not maintain an EASI-50 response (from the parent study baseline) will move to lebrikizumab 250 mg Q2W for the remainder of this addendum.

Addendum schema

This schema summarizes the design of this addendum.

- Starting at Visit 201 of this addendum, patients who do not maintain an EASI-50 response (from the parent study baseline) will move to lebrikizumab 250 mg Q2W dosing regimen for the remainder of this addendum.
- b Patients may enter the addendum
 - at Week 100 of Study KGAA, or
 - after Week 100 of Study KGAA provided they have not yet completed the safety follow-up visit for Study KGAA.
- ^c From KGAA addendum (11) baseline.

2.3.1. Protocol Section 3.1. Duration of the Study

The maximum duration of a patient's participation in this study addendum will be up to 42 weeks (32 weeks of the open-label extension period plus addendum safety follow-up visit 12 weeks following the last injection of study drug).

2.3.2. Protocol Section 3.2. Study Population and Number of Patients

Up to approximately 213 patients are expected to enroll in this study addendum:

- Q4W treatment group: N = 106
- Q8W treatment group: N = 107

2.4. Protocol Section 4. Selection of Patients

2.4.1. Protocol Section 4.1. Inclusion Criteria

Patients must meet all the following criteria to be eligible for this study addendum:

- [1] Have completed Week 100 (Visit 11) of Study KGAA and have not yet completed the safety follow-up visit for the main study.
- [2] Are willing and able to comply with all clinic visits and addendum-related procedures.

[3] For women of childbearing potential: agree to remain abstinent (refrain from heterosexual intercourse) or use a highly effective contraceptive method during the treatment period and for at least 18 weeks after the last dose of lebrikizumab.

NOTE: A woman of childbearing potential (WOCBP) is defined as a postmenarcheal female, who has not reached a postmenopausal state (≥ 12 continuous months of amenorrhea with no identified cause other than menopause) and has not undergone surgical sterilization (removal of ovaries and/or uterus).

NOTE: The following are highly effective contraceptive methods: combined (estrogen and progestogen containing) hormonal contraception (oral, intravaginal, transdermal) associated with inhibition of ovulation, progestogen-only hormonal contraception (oral, injectable, implantable) associated with inhibition of ovulation, intrauterine device (IUD), intrauterine hormone-releasing system (IUS), bilateral tubal occlusion, bilateral tubal ligation, vasectomized partner, or sexual abstinence. The reliability of sexual abstinence should be evaluated in relation to the duration of the clinical trial and the preferred and usual lifestyle of the patient. Periodic abstinence (e.g., calendar, ovulation, symptothermal, or postovulation methods) and withdrawal are not acceptable methods of contraception.

If the highly effective contraceptive methods are contraindicated or strictly declined by the patient, acceptable birth control methods may be considered. These may include a combination of the following methods:

- male or female condom with spermicide, and
- cap, diaphragm, or sponge with spermicide.
- [4] Male patients are not required to use any contraception except in compliance with specific local government study requirements.
- [5] Have given written informed consent for participating in this addendum that has been approved by the ethical review board governing the site prior to any addendum-specific procedures being initiated.

2.4.2. Protocol Section 4.2. Exclusion Criteria

Patients meeting any of the criteria below will not be included in this study addendum:

- [1] Have, during their participation in Study KGAA, developed a serious adverse event (SAE) deemed related to lebrikizumab, which in the opinion of the investigator or of the medical monitor could indicate that continued treatment with lebrikizumab may present an unreasonable risk for the patient.
- [2] During their participation in Study KGAA, developed an AE that was deemed related to lebrikizumab and led to study treatment discontinuation, which in the opinion of the investigator or of the medical monitor could indicate that continued treatment with lebrikizumab may present an unreasonable risk for the patient.
- [3] Developed conditions in Study KGAA consistent with protocol-defined criteria for permanent study drug discontinuation, if deemed related to lebrikizumab or led to

- investigator- or sponsor-initiated withdrawal of patient from the study (e.g., non-compliance, inability to complete study assessments, etc.).
- [4] Have initiated treatment with a medication prohibited by Study KGAA (see Section 6 of the main KGAA protocol) before addendum baseline. This includes use of biologics for AD (for example, dupilumab and tralokinumab) during the safety follow-up period of Study KGAA.
- [5] Are pregnant or breastfeeding women, or women planning to become pregnant or breastfeed during the study.

2.5. Protocol Section 5.3. Study Drug Assignment

Patients eligible to participate in this open-label study addendum will be randomly re-assigned to the Q4W and Q8W treatment groups in a 1:1 ratio.

Participants will be stratified at the addendum baseline by

- IGA score (0,1 vs. >1), and
- region (US vs. non-US).

2.6. Protocol Section 5.4. Study Blinding

This addendum is open label.

2.7. Protocol Section 6. Concomitant Medications and Procedures

See Section 6 of the main KGAA protocol and Exclusion Criterion 4 for this addendum.

2.8. Protocol Section 7. Study Procedures

See the Schedule of Visits and Procedures for this addendum (Section 2.14).

2.9. Protocol Section 8.4. Study Termination

For discontinuation criteria, see the following sections of the main KGAA protocol:

- Section 8.4.1: early termination of study patients

 Exception: The following discontinuation criterion from the main protocol will *not* apply to this addendum: "Not achieving an EASI-50, from parent study baseline, by Week 16, maintaining an EASI-50 response, or not achieving clinical benefit based on PI discretion should be terminated from this study." As indicated in Section 2.3 of this addendum, patients who do not maintain an EASI-50 response (from the parent study baseline) will move to lebrikizumab 250 mg Q2W.
- Section 8.4.3: temporary and permanent discontinuation of study drug

2.10. Protocol Section 9.1. General Statistical Methodology

All statistical processing will be performed using SAS® unless otherwise stated.

Descriptive statistics will be used to provide an overview of the efficacy results. For categorical parameters, the number and percentage of patients in each category will be presented. For

continuous parameters, descriptive statistics will include n (number of patients), mean, standard deviation, median, minimum, and maximum.

Demographic data will be summarized by treatment group using descriptive statistics.

The number of patients in each analysis set will be summarized. Reasons for study withdrawal and treatment withdrawal during the study will be summarized using frequencies and percentages by treatment group.

A statistical analysis plan (SAP), describing all statistical analyses will be provided as a separate document.

2.10.1. Protocol Section 9.1.1. Populations Analyzed

Efficacy analysis will be performed using the ITT population. The ITT population consists of all patients assigned to treatment in this study addendum, even if the patient does not take the assigned treatment, does not receive the correct treatment, or otherwise does not follow this addendum.

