2.10.2. Addendum Baseline Definition

Patients may enter the addendum

- at Week 100 of Study KGAA, or
- after Week 100 of Study KGAA provided they have not yet completed the safety follow-up visit for Study KGAA.

For the efficacy measures, addendum baseline is defined as the last available value before the first injection in this addendum period, which in most cases will be the value recorded at the addendum baseline visit (Visit 200). Efficacy analysis will be reported by visit from the addendum baseline visit to Week 32 of the addendum period. The baseline used to derive efficacy endpoints is the parent study baseline.

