6.1.1. Analysis Populations

Table KGAA.6.1. Analysis Populations

Population	Description
All Entered Patients	All patients who signed informed consent. The All Entered Patients population will be used for tables and/or listings of disposition that include screen failures and inclusion and exclusion criteria.
ITT Population	All patients assigned to treatment, even if the patient does not take the assigned treatment, does not receive the correct treatment, or otherwise does not follow the protocol. Patients will be analyzed according to the treatment to which they were assigned.
mITT Population	ITT population excluding all patients from Site CC and Site CC. This population will be used to summarize patient disposition, demographics, and efficacy analyses, plus to list patient data.
Safety Population	All patients who receive at least 1 confirmed dose of lebrikizumab will be included in the Safety Population.
Modified Safety Population	Safety population excluding all patients from Site CC and Site CC. Demographics, extent of exposure, treatment compliance, prior/concomitant medication use, adverse event, and immunogenicity safety analyses will be performed using the Modified Safety Population.
CCI	

Abbreviations: CC ; ITT = intent-to-treat; mITT = modified intent-to-treat.

- ^a Site CCI only participated in Studies KGAC/AD05, KGAD/AD06, KGAK/AD18, and Site CCI only participated in Study KGAK/AD18. So, analyses with only data from Studies KGAB/AD04, KGAE/AD17, and Protocol KGAA Addendum 1.1 will not be impacted.
- b The rationale for excluding patients from Site CC is in a directed site audit triggered by statistically implausible data in Study KGAD/AD06 at this study site, and the same site was also included in this Study KGAA/AD07. It was determined that some or all of the study patients at this site did not meet the eligibility criterion of having moderate-to-severe atopic dermatitis, and associated data was unreliable.
- The rationale for excluding patients from Site is a clinical site audit of lebrikizumab atopic dermatitis Studies KGAK/AD18 and KGAA/AD07 at this site which resulted in critical findings. It was determined by the audit that there was a lack of source documentation needed to substantiate eligibility for all patients enrolled at this site. Additionally, a quality issue was opened where data relating to patient's moderate-to-severe atopic dermatitis is either unreliable, inconsistent, and/or missing source documentation.

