6.2.2. Estimands of Secondary Objectives (Efficacy)

The secondary clinical question of interest is: what is the proportion of patients who meet the clinical requirements for response AND without discontinuation due to lack of efficacy?

The primary estimand of the secondary objective is described by the following attributes:

- A. Population: modified intent-to-treat (mITT) population as defined in Section 6.1.1;
- B. Variable: apply to all secondary endpoints.
- C. How to account for intercurrent events (ICEs):
 - a. Subjects who discontinued treatment due to lack of efficacy during Study KGAA will be considered as treatment failures, that is, nonresponders, after the ICEs. Therefore, a composite strategy will be used for these types of ICEs.
 - b. For subjects who discontinued treatment due to any other reasons, the hypothetical strategy will be used to estimate what the treatment effect would have been if subjects continued with treatment. Therefore, the hypothetical strategy will be used for these ICEs
- D. Population-level summary: response proportions or means.

The **first supportive estimand of the secondary objective** is described by the following attributes:

- A. Population: mITT population as defined in Section 6.1.1;
- B. Variable: apply to all secondary endpoints.
- C. How to account for ICEs: as observed strategy will be used, that is, only data from completers at the visit are relevant.
- D. Population-level summary: response proportions or means.

The **second supportive estimand of the secondary objective** is described by the following attributes:

- A. Population: modified ITT population as defined in Section 6.1.1;
- B. Variable: apply to all secondary endpoints.
- C. How to account for ICEs: for subjects who discontinue treatment, the hypothetical strategy will be used to estimate what the treatment effect would have been if all subjects adhered to the treatment. Therefore, the hypothetical strategy is used for these types of ICEs.
- D. Population-level summary: response proportions or means.

Analytical details on how missing data, including data missing as a result of intercurrent events, will be handled can be found in Section 6.4. Endpoints will be analyzed as described in Section 6.11 and Section 6.14. No statistical test will be performed.

Table KGAA.6.2. summarizes different analyses that will be conducted on the secondary endpoints.

Table KGAA.6.2. Analysis of Secondary Endpoints

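### Addendum efficacy is set on all assigned patients, without the exclusion of two audited sites that the SAP applies to main-study efficacy

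*Protocol*

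**What the plan says.** **Addendum.** Protocol section 2.10.1 says "Efficacy analysis will be performed using the ITT population" and defines that set without any site restriction: "The ITT population consists of all patients assigned to treatment in this study addendum, even if the patient does not take the assigned treatment". No modified set is named. Section 2.10.2 adds: "The baseline used to derive efficacy endpoints is the parent study baseline". Sections 2.2 and 2.11 make EASI-75 at Week 32, measured against that baseline, one of the two endpoints; the other is IGA 0 or 1. The entry criteria in sections 2.4.1 and 2.4.2 admit patients who completed Week 100 of KGAA and do not mention the audited sites.

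**Main study.** SAP Table KGAA.6.1 defines mITT as "ITT population excluding all patients from Site CC and Site CC" (the site numbers are blacked out) and gives its use: "This population will be used to summarize patient disposition, demographics, and efficacy analyses, plus to list patient data". Section 6.2.2 sets every efficacy estimand on it, the primary one with "Population: modified intent-to-treat (mITT) population as defined in Section 6.1.1".

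**Reasons for the exclusion.** The table's footnotes say that at the first site some or all patients "did not meet the eligibility criterion of having moderate-to-severe atopic dermatitis, and associated data was unreliable". At the second, an audit found no adequate source records to support eligibility for any enrolled patient, and the AD data there are described as unreliable, inconsistent and/or lacking source records. The footnotes place both sites in KGAA itself.

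**The concern.** Two parts of one study use different rules for the same kind of patient. The sponsor decided that data from two sites should not enter efficacy summaries, and the addendum, which draws only on patients already in that study, does not carry the decision over. The SAP lists mITT among its Version 2 changes (12 May 2022). The addendum carries approval stamps of 17 November 2023, so the audit findings were already known, and it gives no reason for using a different set.

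EASI-75 is exposed because its denominator is the parent-study baseline, recorded when the patient's eligibility was judged. The same baseline also enters by a second route. Under section 2.3, loss of EASI-50 against it moves a patient to Q2W dosing, and section 2.2 scores that move as non-response. IGA 0 or 1 has no baseline denominator, but it is exposed if the patient did not have moderate-to-severe AD to begin with.

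The planned output is a descriptive response proportion per arm, and any such patients would enter those proportions directly.

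**Working it through.** **1. Does the exclusion reach the addendum?** Setting the texts side by side:

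- Main-study efficacy set: ITT minus two sites (SAP Table KGAA.6.1, section 6.2.2).
- Addendum efficacy set: all assigned, no site rule (Protocol 2.10.1).
- Source of addendum patients: KGAA completers of Week 100 (Protocol 2.4.1), in seven listed countries (Protocol section 1).
- Parent studies of the two sites: KGAC, KGAD and KGAK for one, KGAK only for the other (Table KGAA.6.1, first footnote). Their patients therefore have parent-study baselines, which is what EASI-75 uses.

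Nothing in the addendum text keeps these patients out. Nothing in either document shows that any came in.

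**2. The plan's own figures.** Protocol 2.13 gives 95% intervals with 106 per arm. The Wald formula, p ± 1.96 × √(p(1−p)/n), gives:

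- Q4W: 0.83 ± 1.96 × √(0.83 × 0.17/106) = 75.8% to 90.2% (stated: 76% to 90%).
- Q8W: 0.69 ± 1.96 × √(0.69 × 0.31/106) = 60.2% to 77.8% (stated: 60% to 78%).

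Both reproduce.

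**3. Effect of leaving the sites in.** The documents give no count, so let k be an assumed number of site patients per arm and r an assumed share of them counted as responders. The remaining patients respond at the hypothesised rate p:

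observed rate = ((n − k) × p + k × r) / n

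with n = 106 for Q4W and 107 for Q8W (Protocol 2.3.2). For k = 5:

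- Q4W: r = 0 gives 101 × 0.83/106 = 79.1%; r = 1 gives (101 × 0.83 + 5)/106 = 83.8%.
- Q8W: r = 0 gives 102 × 0.69/107 = 65.8%; r = 1 gives (102 × 0.69 + 5)/107 = 70.4%.

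| Assumed k per arm | Q4W, true 83% (r = 0 to 1) | Q8W, true 69% (r = 0 to 1) |
|---|---|---|
| 0 | 83% | 69% |
| 2 | 81.4% to 83.3% | 67.7% to 69.6% |
| 5 | 79.1% to 83.8% | 65.8% to 70.4% |
| 10 | 75.2% to 84.6% | 62.6% to 71.9% |

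The shift can go either way. The range reaches further down than up because both hypothesised rates lie well above 50%.

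**4. Cost of taking the sites out.** The same Wald formula with n − k patients:

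| Assumed k per arm | Q4W at 83% (n = 106 − k) | Q8W at 69% (n = 107 − k) |
|---|---|---|
| 5 | 75.7% to 90.3% | 60.0% to 78.0% |
| 10 | 75.5% to 90.5% | 59.8% to 78.2% |
| 15 | 75.3% to 90.7% | 59.5% to 78.5% |

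At k = 15 the limits move by at most about 0.7 points (Q8W: 60.2% to 59.5% and 77.8% to 78.5%).

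**The case against.** **The governing SAP is not to hand.** Protocol 2.10 promises a separate SAP, and 2.12 refers to one for this addendum. The supplied SAP covers the main study: it has no Q8W arm and its efficacy analyses end at Week 100. The main-study exclusion was itself introduced by an SAP revision, so the addendum SAP may contain it too. This stands as a limit on what can be concluded. If that SAP does restore mITT, Protocol 2.10.1 still names a different set and the two need reconciling.

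**No affected patient is shown.** The site identities are blacked out, only seven countries take part, and entry is possible up to 10 weeks after Week 100. Counting back 110 weeks from the November 2023 approval, only patients who entered KGAA from about early October 2021 could qualify. This narrows the pool without emptying it: both sites took part in KGAK, and nothing in the documents dates those patients' entry outside the window.

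**The contrast is randomised and untested.** Assignment is 1:1, so systematic imbalance between arms is not expected, and no test is planned. That is correct, but it does not protect the per-arm proportions, which are what will be reported.

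**Stronger readings that the documents do not support.** A reader might infer that such patients, having perhaps had milder disease, would nearly all respond and so raise both arms. That assumes r = 1. A patient with a genuinely low recorded baseline could find a 75% reduction harder to show, while an inflated baseline would make it easier. A reader might also infer that the audits discredited baseline EASI itself. The footnotes speak of eligibility and of AD data and never name that measurement; its involvement is an inference.

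**Conclusion.** The inconsistency is real. The addendum's efficacy set lacks a site exclusion that the same study's SAP applies to all main-study efficacy estimands, and the addendum text does not keep those sites' patients out. If any enrolled, the Week 32 IGA and EASI-75 proportions would include data the sponsor has already set aside.

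Actual contamination is not shown, and the effect is zero if neither site contributed a patient. If they did, both size and direction are unknown. At an assumed 5 patients per arm, the shift lies between about −3.9 and +0.8 points for Q4W (79.1 − 83 and 83.8 − 83) and between about −3.2 and +1.4 points for Q8W (65.8 − 69 and 70.4 − 69). Those figures rest on the Protocol's hypothesised rates, an assumed count, and the two extreme response shares.

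The point is a cheap improvement: the rule already exists, applying it costs almost no precision, and the sponsor can settle the open fact from its own records.

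**What to change.** Either of two changes closes the point:

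1. Define the addendum efficacy set as the addendum ITT population minus patients from the two sites excluded from mITT, using the Table KGAA.6.1 definition. Report full ITT as a sensitivity analysis and list the excluded patients.
2. If no patient from either site entered the addendum, say so, and leave ITT as it is.

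The wording belongs in the addendum SAP, with Protocol 2.10.1 brought into line or cross-referenced. The cost is a few lines of text and, under the first option, a small loss of patients with the negligible effect on precision shown above. Keeping full ITT as a sensitivity analysis means that nothing is hidden by the exclusion.
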